6.3. Trial design

7. Centralized biological study (hepcidine, LPI, NTBI)

Serum hepcidin assay:

Serum hepcidin will be measured with a previously validated LC-MSMS method (Thibaud Lefebvre et al, Clin Chem Lab Med 2015). 200 μ l of serum samples will be pre-treated by solid phase extraction. Then, hepcidin will be separated on C18 column by ultra high-pressure chromatography (Acquity UPLC - Waters) and detected by MS/MS on a Xevo TQMS (Waters). (13C1815N3)-Hepcidin-25 (PeptaNova GmbH, Sandhausen, Germany) will be used as an internal standard. The method was found to be linear over the analytical range of 1,5 to 200 μ g/L (R2 > 0.99). Undetected values for hepcidin (< 0.75 ng/mL) are imputed using a beta law.

Serum NTBI assay:

Total content of Non-Transferrin Bound Iron (NTBI) will be measured by the FeROSTM eLPI kit. This assay measures the iron-specific redox activity in serum. The Reactive Oxygen Species (ROS) will be detected by an oxidation-sensitive probe (DHR), which becomes fluorescent when oxidized by ROS. The assay employs a control reaction where a selective iron chelator blocks redox cycling of iron to specifically identify iron-mediated ROS generation. Comparison of the kinetics of fluorescence generated in the reaction in the presence and absence of the iron chelator provides measure of the total NTBI content.

Iron status measurement:

Serum samples will be used to measure iron, transferrin, ferritin, soluble transferrin receptor and CRP concentrations by routine hospital technology.

8. Study procedures

8.1. At inclusion

After checking the inclusion and exclusion criteria, as well as parameters necessary for stratification, the investigator will request inclusion online.

The following information will be collected:

- Medical history: date of diagnosis and initial disease characteristics (blood counts, bone marrow results, cytogenetic analysis)
- Previous treatments and history of RBC and platelet transfusions

Then, the investigator will:

- Check inclusion criteria
- For young patients, 18-45 years, contact [name] by e-mail ([contact])

- Collect the informed consent (clinical +/- biological study)
- Perform clinical examination: weight, height, PS (ECOG, Appendix 1), co-morbidity (Appendix 2-3)
- Perform baseline blood tests including: full blood count and differential, including peripheral blasts count and reticulocytes, AST, ALT, serum bilirubin, LDH, PAL, GGT, creatinine, EPO level, CRP, B12 and folates test
- Urine test: proteinuria
- Perform bone marrow aspiration for morphology, cytogenetics, and correlative biological studies (2 mL EDTA). If this analysis has been done within the 2 months prior to inclusion and if peripheral blood cell counts are stable: a new bone marrow aspiration could be avoided if BM sample have been sent to the CHRU of Lille, [name] laboratory, and SMD molecular analysis have already been performed (ASXL1, TP53, EZH2, ETV6, RUNX1...)
- Send bone marrow (2 ml EDTA) and blood (10 ml EDTA) samples for molecular analysis
- Send serum, 10 ml (2 tubes 5 ml without EDTA or citrate), before Exjade[®] initiation, to Louis Mourier Hospital for iron biological study
- HLA will be performed in these patients and in their siblings (if available and age < 70 years without cancer, thrombosis or cardiac failure history). If no donor is available among siblings, a matched unrelated donor 8/8 unrelated donor is searched. Antibodies against HLA should also be checked.
- Iron overload will be estimated at registration by the number of transfusions received since initial diagnosis, iron parameters (serum iron, transferrin saturation, serum ferritin)
- **Heart and liver MRI** should be performed within 6 weeks in patients with iron chelation criteria: ferritin level > 1000 ng/mL (can be done also before inclusion, maximally 6 weeks before)
- Pregnancy test, if applicable
- Quality of life questionnaire (EORTC)

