3.2 Secondary Objectives

- ✓ Comparison between patients with or without a donor for:
 - a. Cumulative incidence of complete response at 36 months
 - b. Cumulative incidence of Transformation in AML at 36 months (according to WHO criteria, > 20% blasts in peripheral blood or bone marrow)

Evaluate:

- ✓ Risk factors for outcome (remission, mortality)
- Risk factors for overall survival (age, disease characteristics...) including iron overload (ferritin, plasmatic iron markers, MRI)
- ✓ The efficiency of chelation will be assessed at 3 months after inclusion for all patients
- ✓ Feasibility of the transplant define by the proportion of patients with a donor who undergo the transplantation (expected between 80 and 95%)
- ✓ Proportion of patients with iron overload (Serum Ferritin (SF) > 1000 ng/mL or RBC transfusion > 20) at time of inclusion and at 16 months after inclusion for non-transplanted patients and 12 months post-transplant for transplanted patients
- ✓ The effect of chelation post-transplant will be measured by SF level: SF < 1000 ng/mL, SF > 1000 ng/mL, SF > 1500 ng/mL and also by percentage of patients with SF decrease of at least 30%
- Eligibility of post-transplant Exjade[®] treatment defined by the proportion of patients with iron overload who can benefit from Exjade[®] after the transplantation (% of patients without contraindication to Exjade[®] 3 months after transplant) and who can maintained it at least 6 months or until SF < 700 ng/mL
- ✓ Assessment of change of Ferritin level (% of decrease) and MRI at 12 months post-transplant
- Evolution of innovative iron markers including Non-transferrin binding iron (NTBI), labile plasmatic Iron (LPI) and Hepcidine at time of inclusion (before Exjade®), at 3 months (patients potentially treated by Exjade®) and 16 months post-inclusion for all patients; in transplanted patients these markers will be measured just before conditioning regimen (J-5), just before the transplantation (J0), at D7, 30, 100 and 12 months after transplant. All these markers will be tested as risk factors for outcome (survival, non-relapse mortality and progressive disease)
- ✓ Quality of Life study (EORTC questionnaire at registration, 12, 24 and 36 months)
- ✓ Grade III or IV toxicity (hematological and non-hematological) recorded according to NCI CTC criteria version 4.0
- ✓ Cumulative incidence of severe infection at 12 months

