6.1. Group A: Patients with a donor

- Iron chelation

Patients with iron overload defined as more than 20 blood cell transfusions (since initial diagnosis) or ferritin level > 1000 ng/mL will start Exjade® at 20 mg/kg per day of deferasirox dispersible tablets or 14 mg/kg per day of deferasirox film-coated tablets (when converting a patient from deferasirox dispersible tablets to deferasirox film-coated tablets, the dosage should be decreased by 30%) or will continue Exjade® if they were receiving it before inclusion at a minimal dosage of 20 mg/kg of deferasirox dispersible tablets or 14 mg/kg of deferasirox film-coated tablets or same dose if they were receiving a higher dose. Exjade® will be temporarily discontinued one day before conditioning regimen start or at any moment in case of renal failure (clearance < 60 ml/min). In those patients, Exjade® will be restarted on day 100 in patients with LIC > 5 mg Fe/gr dry weight (defined before the transplantation), except in cases of contraindications including gastro-intestinal disorder (nausea, vomiting, abdominal pain or diarrhea), renal failure (clearance < 60 ml/min), active GVHD, neutropenia < 0.5 G/L, thrombocytopenia < 30 G/L, total bilirubin, AST, ALT > 2xULN, GGT and PAL > 3xULN.

Before restarting Exjade[®], complete iron measurements will be repeated (serum iron, serum ferritin, transferrin saturation, NTBI, LPI, hepcidine) and MRI.

The initial dose of Exjade[®] after transplant will be 10 mg/kg/day of deferasirox dispersible tablets or 7 mg/kg per day of deferasirox film-coated tablets progressively increased to 20 mg/kg/day or 14 mg/kg/day respectively if good tolerance.

Patients with iron overload will be evaluated at each visit by serum ferritin, transferrin and iron in serum; will be evaluated 12 months after transplant by complete iron measurements including serum iron, serum ferritin, transferrin saturation, NTBI, LPI and hepcidine.

Hepcidine and non-transferrin binding iron will be measured in the ancillary biological study (Hôpital Louis Mourier, see appendix 10).

As soon as ferritin reached a level < 700 ng/mL, Exjade[®] will be discontinued.

- Transplantation (D0)

The HSCT should be **scheduled 4 months after the inclusion** either with an HLA-matched sibling or a 8/8 (A,B,C,DRB1) HLA matched unrelated donor.

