6.2. Group B: Patients without a donor

- Iron chelation

[figure not shown]
Iron chelation will be started if baseline ferritin level > 1000 ng/L or in those receiving more than 20 RBC units (or continued if they already received it). Exjade[®] will be started at 20 mg/kg per day of deferasirox dispersible tablets or 14 mg/kg per day of deferasirox film-coated tablets (when converting a patient from deferasirox dispersible tablets to deferasirox film-coated tablets, the dosage should be decreased by 30%) or will continue if they were receiving it before inclusion at a minimal dosage of 20 mg/kg of deferasirox dispersible tablets or 14 mg/kg of deferasirox film-coated tablets.

- Other treatment

Patients can benefit from any treatment including phase II prospective studies, or a treatment considered as the best available treatment. There are no unapproved medications which are tested in this trial.

If the disease evolves to a higher risk by acquiring new cytogenetic abnormalities, new cytopenia or an increase in marrow blast including a transformation into AML, a transplant using an alternative donor should be considered (mismatch unrelated donor, unrelated cord blood or mismatch related donor including haplo-identical transplant), if possible in the setting of a trial assessing alternative transplant.

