- Chronic GVHD should be noticed according to the NIH classification (Appendix 7), only the first episode but the dosage of corticosteroids and the type of immunosuppressive therapy should be collected in the electronic CRF - **Heart and liver MRI** 12 months after transplant in patients with iron overload at inclusion

All patients will be followed at least 24 months according to each center policy. After 24 months, disease status (transformation into AML, progression after transplant, persistent complete remission after transplant) and death (date and cause) will be collected until the end of the protocol.

0.3.1.	Diary to	i transp	ianteu p		Jioup Aj					
Time from HSCT	Screening D-120 M-4	D-90 M-3	D-60 M-2	D-30 M-1	D0 HSCT	D30 M1	D60 M2	D120 D240 M4-M8	D240 D960 M8-32	D480 M16
Inform consent	х									
Clinical visit	x	X2/ M	x	x	x	х	x	X Every 2 months	X Every 3 months	x
Comorbidity assessment	x			х						
ECOG	х	x	x	х	х	х	х	x	х	х
Blood cell counts (9)	x	X1/ W	X1/M	X1/M	X1/M	X1/M	X1/M	X1/M	X1/M	X1/M
Standard biology (1)	х	х	х	х	х	х	х	х	х	х
EPO, folates, B12	х									
Iron plasmatic dosage (2)	x	x	x	x	x	x	x	x	х	x
HLA typing (3)	х	х	х							
Centralized biological study (4)	Х*			D-5 Pre- Allo	D0 before HSCT	D7 and D30 post allo		D 100 post Allo		M12 post- Allo
Proteinuria	х	х	х	х	х	х	х	x	х	х
Bone marrow aspiration + blood + cytogenetics (5)	x							D100 post Allo	M12, 24 &36 post inclusion	
Heart and liver MRI (6)	x			x				Х*		M12 post allo
QOL	x								M12, 24 &36 post inclusion	
AE Grade III-IV	x	x	х	x	x	x	х	x	x	х
Pregraft tests (7)			x							
GVHD assessment						x	Х	x	Х	Х
Postgraft blood chimerism (8)						x	Х*	X*	Х*	
Confirming date of HSCT		x	x	x						

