8.3. Diary8.3.1. Diary for transplanted patient (Group A)

8.3.2.	Diary for NON-Tran	planted patient	(Group B)
--------	---------------------------	-----------------	-----------

Time from registration	D0 Screening	D30 M1	D60 M2	D90 M3	D120 M4	D150 M5	D180 M6	D240 D365 M8- M12	D365 D990 M12-M33	D1080 M36
Inform consent	х									
Clinical visit	x	X2/ M	x	х	x	x	x	X Every 2 months	X Every 3 months	x
Comorbidity assessment	x			x						
ECOG	х	х	х	х	х	х	х	х	х	х
Blood cell counts (9)	x	X1/ W	X1/M	X1/M	X1/M	X1/M	X1/M	X1/M	X1/M	X1/M
Standard biology (1)	х	х	х	х	х	х	х	х	х	х
EPO, folates, B12	х									
Iron plasmatic dosage (2)	x	x	x	x	x	x	x	x	x	x
HLA typing (3)	х	х	х							
Centralized biological study (4)	Х*			x					M16	
Proteinuria	х	х	х	х	х	х	х	х	х	х
Bone marrow aspiration + blood + cytogenetics (5)	x								M12 &24	x
Heart and liver MRI (6)	x			x						
QOL	x								M12 & 24	x
AE Grade III-IV	x	x	х	х	x	x	x	x	x	х

(1) Every visit: Proteinuria, AST, ALT, serum bilirubin, serum creatinine, PAL, LDH, GGT, CRP

(2) Serum ferritin, transferrin, iron plasmatic level

(3) HLA A, B, C, DRB1 molecular level

(4) Centralized study – 2 tubes without EDTA 5 mL to Louis Mourier Hospital, see specificity in appendix 10. *Before Exjade initiation (5) Inclusion, D60 to D100 post-transplant or once a year for non-transplant patient. Including cytogenetic and centralized shipment

for molecular analysis to CHRU Lille (BM 2 ml EDTA + Blood 2 tubes 5 mL with EDTA)

(6) Only for patients with SF > 1000 ng/mL or more than 20 RBC transfusions at time of inclusion. At time of screening, could be done within 6 weeks before or after inclusion. *After transplant, should be done at D100 and before Exjade restarting

(7) Include cardiac and pulmonary assessment

(8) Assessment at D30. *Should be repeated at the next visits only if the first one is not donor > 95% or in cases a rejection is suspected

(9) Including reticulocytes and blast count

9. Statistical analysis

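### The inclusion-MRI instruction in Protocol 8.1 gives the iron chelation criteria as ferritin alone and drops the more-than-20-transfusions route stated in 3.2, 6.1, 6.2 and diary footnote 6

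*Protocol*

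**What the plan says.** Five parts of the Protocol bear on who has the inclusion MRI.

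- **8.1, At inclusion.** The scan is to be done within 6 weeks "in patients with iron chelation criteria: ferritin level > 1000 ng/mL"; it may also be done up to 6 weeks before inclusion. No transfusion count is given in this bullet.
- **6.1, Group A.** Chelation is started or continued in "Patients with iron overload defined as more than 20 blood cell transfusions (since initial diagnosis) or ferritin level > 1000 ng/mL".
- **6.2, Group B.** Chelation is started on baseline ferritin above 1000 (printed there as ng/L) or "in those receiving more than 20 RBC units".
- **3.2, Secondary Objectives.** Iron overload is defined by the same two alternatives, ferritin above 1000 ng/mL or more than 20 RBC transfusions.
- **Footnote 6 to the MRI row** (8.3 diaries, repeated in Appendix 11). The scan is "Only for patients with SF > 1000 ng/mL or more than 20 RBC transfusions at time of inclusion". The footnote goes on to cover the screening scan, with a window of 6 weeks either side of inclusion.

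On the use of the data, 3.2 says: "The efficiency of chelation will be assessed at 3 months after inclusion for all patients". It also lists MRI among the iron-overload risk factors for overall survival.

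**The concern.** Section 8.1 names the chelation criteria and then spells them out as one criterion where the rest of the Protocol has two. It is the list a site works through at inclusion, so the shortened version may be the one that is followed. A patient who qualifies for chelation by transfusion count alone would then receive Exjade under 6.1 or 6.2 without the inclusion MRI that footnote 6 calls for.

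A scan that was not done cannot be recovered at analysis. At stake is the inclusion MRI value in these patients, for the secondary analyses of iron overload and chelation.

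**Working it through.** The Protocol gives no figure to reproduce here. The check sets the two rules side by side and then counts the scheduled scans.

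**Step 1. Who is scanned at inclusion under each rule**

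| Ferritin (ng/mL) | RBC transfusions | Chelation criterion met (6.1, 6.2) | Inclusion MRI, footnote 6 | Inclusion MRI, 8.1 |
|---|---|---|---|---|
| > 1000 | > 20 | yes | yes | yes |
| > 1000 | ≤ 20 | yes | yes | yes |
| ≤ 1000 | > 20 | yes | yes | **not listed** |
| ≤ 1000 | ≤ 20 | no | no | no |

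The rules differ in the third row only. Patients whose ferritin is high and whose transfusion count is low also have discordant markers, but 8.1 still scans them.

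**Step 2. Scans left if the inclusion scan is omitted in a third-row patient**

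- Group A diary: screening (D-120), D-30, D100 and 12 months post-transplant, so 4 scans. Without the first, 4 − 1 = 3.
- Group B diary: D0 and D90, so 2 scans. Without the first, 2 − 1 = 1, and no within-patient MRI change can be computed.

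**Step 3. Can the next scan stand in for the inclusion scan?**

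- Transplant is "scheduled 4 months after the inclusion", which the diary shows as D-120. D-30 is therefore day 120 − 30 = 90 after inclusion, the same time as the group B scan at D90.
- The inclusion window closes at 6 × 7 = 42 days. Day 90 is 90 − 42 = 48 days later.
- Section 3.2 schedules the serum iron markers "at time of inclusion (before Exjade®), at 3 months (patients potentially treated by Exjade", so month 3 is a time when Exjade may already be in use.

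The day-90 scan is thus a later, possibly on-treatment, measurement and not a replacement for the inclusion scan. In group A it is still a pre-transplant scan. It can supply the liver iron content that 6.1 uses for the day-100 Exjade restart, and a comparator for the 12-month scan.

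**Step 4. Is the inclusion scan itself a pre-chelation baseline?**

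Not necessarily. Section 8.1 and footnote 6 both allow it up to 6 weeks after inclusion, and nothing requires it before Exjade starts. Only the serum sample is tied to the time before Exjade initiation (8.1, footnote 4). Patients already on Exjade at inclusion have no pre-chelation scan in any case.

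**The case against.** The strongest reply is that 8.1 is shorthand. Its operative words point to the chelation criteria, which 6.1 and 6.2 set out in full. The bullet just before it counts transfusions when estimating iron overload. It does not say that only high-ferritin patients are scanned, whereas footnote 6 does say who alone is scanned and addresses the screening scan directly. A site can satisfy both texts by scanning everyone in footnote 6, and a site that uses the diary row for the later scans would see the screening scan under the same footnote.

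Much of this stands. It means that omission is possible, not certain. It does not make 8.1 correct: a colon followed by one criterion reads as a definition, and that definition is incomplete.

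The objection also stands on the link to the objectives. Section 3.2 does not name MRI as the measure of chelation efficiency at 3 months, and ferritin is taken at every visit. Nor does it say that the MRI risk factor must be the inclusion value.

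A reader might infer three stronger points, none of which the Protocol supports:

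- That the inclusion MRI is lost wherever ferritin and transfusion load disagree. Only one of the two discordant groups is exposed.
- That a guaranteed pre-chelation MRI is lost. The permitted window does not guarantee one.
- That the day-100 restart in group A lacks its liver iron value. The D-30 scan supplies it.

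**Conclusion.** Section 8.1 is wrong as written and conflicts with 3.2, 6.1, 6.2 and both copies of footnote 6. The effect is minor. The inclusion MRI might be missing in patients with ferritin at or below 1000 ng/mL and more than 20 RBC transfusions. In group B this could leave only the D90 scan; in group A three of four scans remain.

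This assumes that a site follows 8.1 for the inclusion scan and the diary for the later ones. The Protocol does not give the number of such patients, and none is assumed here. Only secondary iron analyses are touched. The overall survival comparison and the sample size do not depend on MRI.

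**What to change.** In the MRI bullet of 8.1, replace the ferritin-only criterion with: ferritin level > 1000 ng/mL or more than 20 RBC transfusions since initial diagnosis. This is one phrase, and no scan is added.

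Optional tidying at the same time: use one term for the count in 6.1 (now blood cell transfusions) and 6.2 (now RBC units), and print the 6.2 ferritin threshold in ng/mL instead of ng/L.

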8.2. Visits

For all enrolled patients, visits will be performed:

- at inclusion
- every two weeks during the first 4 weeks (first month)
- every 4 weeks from the 5th week to the 26th week (until 6th month)
- every 8 weeks from the 27th week to the 52th week (until 12th month)
- every 12 weeks from the 53th week to the end of study.

At each patient visit, the following information will be registered:

- Grade III to IV adverse events (classified according to NCI- CTCAE 4.0) http://evs.nci.nih.gov/ftp1/CTCAE/CTCAE_4.03_2010-06-14_QuickReference_5x7.pdf

- Treatment by Exjade[®] and its dose
- Clinical assessment (every 2 weeks on first month)
- Weight, PS, serious infectious disease (defined in Appendix 4)
- Transfusion history (platelet and RBC) including the research of allo-immunisation (RAI)
- AST, ALT, serum bilirubin, serum creatinine, PAL, LDH, GGT, CRP

- Proteinuria (rapid urine test)

- Pregnancy test, if applicable
- Blood cell count including reticulocytes (every week during the 1th month then every 4 weeks)
- Ferritin level, transferrin level and saturation, plasmatic iron level
- In case of disease progression/relapse suspicion, marrow + cytogenetic analysis

Specific information for specific point (after inclusion):

- Quality of life questionnaire (EORTC) at 12, 24 and 36 months

- Centralized biological study (hepcidine, LPI, NTBI): At 3 and 16 months after inclusion (specific form in Appendix 10)

- **Bone marrow aspiration** with cytogenetic (local laboratories) and molecular biology (CHRU Lille) will be performed according to local policy but at least once a year

For patients who received a transplant:

- Pre-graft tests including cardiac assessment and respiratory assessment with pulmonary tests

- **Centralized biological study (hepcidine, LPI, NTBI):** just before conditioning regimen (D-5), just before transplant on day 0, and on day 7, 30, 100, 365 post-transplant

- Between 2 to 3 months after the transplant, a **bone marrow aspiration** (with shipment for biological study: BM 2 ml EDTA)

- At least one post-transplant **chimerism** in blood after engraftment on day 30. The chimerism will be repeated only if the first one is not donor > 95% or in cases a rejection is suspected

- Acute GVHD grade per organ at each visit (Appendix 6)

- Neutrophil engraftment and platelet engraftment (within 60 days post-transplant)

- Chronic GVHD should be noticed according to the NIH classification (Appendix 7), only the first episode but the dosage of corticosteroids and the type of immunosuppressive therapy should be collected in the electronic CRF - **Heart and liver MRI** 12 months after transplant in patients with iron overload at inclusion

All patients will be followed at least 24 months according to each center policy. After 24 months, disease status (transformation into AML, progression after transplant, persistent complete remission after transplant) and death (date and cause) will be collected until the end of the protocol.

0.3.1.	Diary to	i transp	ianteu p		Jioup Aj					
Time from HSCT	Screening D-120 M-4	D-90 M-3	D-60 M-2	D-30 M-1	D0 HSCT	D30 M1	D60 M2	D120 D240 M4-M8	D240 D960 M8-32	D480 M16
Inform consent	х									
Clinical visit	x	X2/ M	x	x	x	х	x	X Every 2 months	X Every 3 months	x
Comorbidity assessment	x			х						
ECOG	х	x	x	х	х	х	х	x	х	х
Blood cell counts (9)	x	X1/ W	X1/M	X1/M	X1/M	X1/M	X1/M	X1/M	X1/M	X1/M
Standard biology (1)	х	х	х	х	х	х	х	х	х	х
EPO, folates, B12	х									
Iron plasmatic dosage (2)	x	x	x	x	x	x	x	x	х	x
HLA typing (3)	х	х	х							
Centralized biological study (4)	Х*			D-5 Pre- Allo	D0 before HSCT	D7 and D30 post allo		D 100 post Allo		M12 post- Allo
Proteinuria	х	х	х	х	х	х	х	x	х	х
Bone marrow aspiration + blood + cytogenetics (5)	x							D100 post Allo	M12, 24 &36 post inclusion	
Heart and liver MRI (6)	x			x				Х*		M12 post allo
QOL	x								M12, 24 &36 post inclusion	
AE Grade III-IV	x	x	х	x	x	x	х	x	x	х
Pregraft tests (7)			x							
GVHD assessment						x	Х	x	Х	Х
Postgraft blood chimerism (8)						x	Х*	X*	Х*	
Confirming date of HSCT		x	x	x						

